Official Title: Use of Dermabond in Mitigation of Spinal Cord Stimulation Trial Lead Migration

NCT05914311

IRB Approval Date: 08/05/2025

Use of Two Standards of Care: Dermabond versus Suture in Mitigation of Spinal Cord Stimulation Trial Lead Migration

Principal Investigator, Co-investigator(s): [name] (PI); ; [name] MD; [name] MD; [name] MD PhD

Sponsor or funding source: Department of Anesthesiology at Atrium-Health Wake Forest Baptist Medical Center

Background, Rationale and Context

Spinal Cord Stimulation is a FDA approved and effective treatment for chronic pain. It is indicated in patients with varying medical conditions ranging from neuropathic pain syndromes to failed back surgery syndrome.¹ A prognostic test (trial) is required prior to the permanent implantation of a Spinal Cord Stimulation (SCS) system. The Spinal Cord stimulator 'trial' (prognostic tests) requires precise placement of SCS leads in the thoracic epidural space to capture the pain areas including the low back and lower extremities.¹ Standard medical practice is to place two SCS leads per patient treated to obtain appropriate neuroanatomical coverage. Since the leads are not anchored into the deep tissue (thoracolumbar fascia), migration of the leads can occur and result in suboptimal trial resulting in a technical failure of the prognostic test increasing the possibility of false negative results. Migration of the SCS leads can result in up to 2.49 mm to 3.24 mm migration in the leads depending on trial length.^{2,3} Early studies on SCS leads placed percutaneously demonstrates migrations rates occurring in 13.2 to 69.2% of cases.^{4,5} During the trial the distal end of the leads are within the thoracic and lumbar epidural space, and the proximal end of the leads are externalized and can be prone to migration. The leads are typically secured in place with tape alone or tape and suture and/or dermabond.

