The suture is a silk sterile surgical suture material. Dermabond is a quick drying adhesive that is currently utilized for assisting in the closure of medical incisions with minimal risk. The use of Dermabond has not been formally investigated but is in common use for securing SCS 'trial' leads. It is unknown which standard of care mechanism of securing SCS trials leads is superior in reducing lead migration. One may be more effective alternative to decrease the incidence of such lead migration, thereby allowing for improvement of outcomes during spinal cord stimulation trial lead placement (in anticipation of surgical placement of spinal cord stimulators for the treatment of chronic pain).

Objectives

Main objective

Determine if the use of Dermabond plus suture as compared to suture alone at the insertion site of a trial spinal cord stimulator lead will lead to less lead migration at the end of the trial period (typically 5-8 days).

Additional Objectives

1. Assess if lead migration changes effectiveness of 'trial'
2. Compare patient satisfaction between patients with migration and without

3. Assess trial lengths effects 5 versus 6 versus 7 versus 8 days on lead migrations rates
4. Determine if there is a change in lead position when using Dermabond plus suture vs suture alone when laying prone on the operating table and then standing and having a PA x-ray performed with radiology

Methods and Measures

Design

All patients who are being considered for a permanent spinal cord stimulator placement are required to have spinal cord stimulator 'trial' leads placed to ensure they are an appropriate candidate for treatment with this device. These trial leads are placed by pain medicine physicians in the pain centers and are secured with either tape and suture, or tape and a combination of Dermabond with suture. Security is at the discretion of the inserting physician. Currently it is not known which method is the best method of securing trial leads to prevent lead migration.

Interventions and Interactions

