This study will be a controlled trial of the two standard of care methods of securing SCS leads in which the trial leads (left and right) will be secured with 1 lead being secured with a suture only while the 2nd lead will be secured after placement with both a suture in addition to Dermabond. All other factors in the SCS trial lead placement will be unaffected by this study. In this manner, the patient will serve as their own control. This will limit confounding factors between patients that may predispose them to migration based on body habitus, sheer forces of back musculature, and other physical attributes that could augment lead migration. In the standard of care SCS 'trials', one lead is typically place to the left of midline (1-2 cm from midline), and another lead to the right of midline (1-2 cm from midline). Although, the anatomy of the two placement location should be identical, we will randomize which lead (left or right) in each patient gets suture plus Dermabond versus suture only to limit any potential procedural (though unlikely) bias in which SCS lead gets secured in a certain fashion. This is within participant randomization. Demographics of the subject to be retrieved include the following: Age, BMI, height, weight, race, ethnicity, history of spine surgery, sex at birth. We will also collect the radiological information required to meet the study objective of this protocol.

As is the standard of care with this subject population, once procedure is completed on Day 0, the patient will be sent for X-ray imaging right after the trial as well as between days 5-8 post procedure. During this second X-ray, the placement of the leads will be evaluated by measuring the amount of lead migration by a physician not involved in the trial. Lead migration will be measured in millimeters from original placement on X-ray imaging. Of note, imaging is obtained during the placement of the trial leads via fluoroscopy. Depending on the location,

the post trial images may be done via x-ray imaging or via fluoroscopy. Either radiological studies are acceptable methods to be used in the analysis of lead migration for this study. The average and median mm of migration per trial will be compared between the two mechanisms of securing the lead. The rate of migration is defined as greater than 4 mm between the two groups. Patient satisfaction survey will also be reviewed upon lead removal by a member of the study team.

Setting

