This will be a single center, academic setting at Atrium Wake Forest Baptist with the Pain Service Line.

Subjects selection criteria

- **Inclusion Criteria**

Any patient presenting to the Pain Service Line for SCS 'trial' lead placement in the thoracic spine defined as terminal tip end in the thoracic spine.

- **Exclusion Criteria**

Allergy to Dermabond and/or Suture material.

Inability to place two leads in the patient.

Lead placement outside of the thoracic spine

- **Sample Size**

Assuming the mean lead migration for use of Dermabond is 2.49 mm compared to mean non-Dermabond usage of 3.24mm, with variance of 1mm, total sample size need for study with study power of 80% with 95%CI for 2-tail test is 56 for both the groups. Lead migration is estimated to occur at a rate of about 13.2% and this number would provide enough analysis to determine if there is a difference in the rates of migration between the groups. No interim analysis will be performed as there is no potential significant harm to the patient and both approaches are standard of care.

Outcome Measure(s)

- **Primary Outcome Measure**

Migration rate of trial leads anchored with Dermabond + suture versus suture alone.

- **Title:** Migration rate of trial leads anchored with Dermabond + suture versus suture alone
- **Description:** Change in 'trial' lead position as measured in millimeters when comparing initial x-ray after placement versus x-ray taken at lead removal 5-8 days after placement.
- **Time Frame:** 5-8 days after placement of trial lead

- **Secondary Outcome Measure**

- **Title:** Number of patients who received pain relief from the SCS 'trial'
- **Description:** Number of responders to the prognostic lead placements defined as >50% pain relief over the length of the trial.
- **Time Frame:** 5-8 Days after placement of trial leads

- **Secondary Outcome Measure**

- **Title:** Patient satisfaction
- **Description:** Lower satisfaction in patients that had lead migration versus patients that did not
- **Time Frame:** 5-8 Days after placement of trial leads

- **Secondary Outcome Measure**

- **Title:** Effect of length of trial on migration
- **Description:** Does a longer trial predispose to a higher rate of infection within a 5-8 day period
- **Time Frame:** 5-8 Days after placement of trial leads

- **Secondary Outcome Measure**

- **Title:** Prone fluoroscopy vs upright PA x-ray

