- **Description:** Difference in lead position on prone fluoroscopy versus upright PA x-ray when comparing Dermabond plus suture versus suture only at lead insertion site
- **Time Frame:** 5-8 Days after placement of trial leads

Analytical Plan

Results will be analyzed initially using descriptive statistics. Comparison between groups will be done using chi square tests for proportions, and t-tests or ANOVA procedures for continuous variables. Regression analysis will be performed to identify independent outcome predictors. Other inferential statistical analysis will be conducted as appropriate.

Human Subjects Protection

Subject Recruitment Methods

All patients undergoing percutaneous SCS trial at Atrium Health - Wake Forest Baptist will be invited to participate in this study. All records will be kept in a secure locked location. Any electronic files will be maintained behind the medical center firewall with password protection. All information collected are de-identified without any patient specific information that can be identifiable to a particular patient.

If any collected patient identifying information corresponding to the unique study identifier will be utilized a linkage file will be stored separately from the data. The linkage file will be kept secure, with access limited to designated study personnel. Following data collection subject identifying information will be destroyed within 6 years.

Confidentiality will be protected by collecting only information needed to assess study outcomes, minimizing to the fullest extent possible the collection of any information that could directly identify subjects, and maintaining all study information in a secure manner. To help ensure subject privacy and confidentiality, only a unique study identifier will appear on the data collection form. Any collected patient identifying information corresponding to the unique study identifier will be maintained on a linkage file, store separately from the data. Data and records will be kept locked and secured, with any computer data password protected. No reference to any individual participant will appear in reports, presentations, or publications that may arise from the study.

Informed Consent

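### Satisfaction is compared between patients with and without migration although migration is measured in millimetres; a graded effect would be tested inefficiently, and patient-level migration is undefined

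*Combined protocol and SAP*

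**What the plan says.** Under Interventions and Interactions: "Lead migration will be measured in millimeters from original placement on X-ray imaging". Each patient has two leads, one per securing method, so there are two readings per patient.

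Additional Objectives, item 2, is to "Compare patient satisfaction between patients with migration and without". The Patient satisfaction outcome under Outcome Measure(s) repeats the two-group form: "Lower satisfaction in patients that had lead migration versus patients that did not".

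The only cut-point is under Interventions and Interactions: "The rate of migration is defined as greater than 4 mm between the two groups". The two groups there are the securing methods. No section carries 4 mm over to patients, says how two leads make one migrated patient, or gives a reason for 4 mm.

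The Analytical Plan says: "Comparison between groups will be done using chi square tests for proportions, and t-tests or ANOVA procedures for continuous variables". It adds a regression to find independent predictors of outcome, without naming outcomes, predictors or the form in which migration enters, and allows other inferential analyses as appropriate.

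Additional Objectives, item 1, reads only "Assess if lead migration changes effectiveness of 'trial". It states no split.

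**The concern.** Splitting a millimetre measurement at one point treats 3.9 mm like 0.5 mm and 4.1 mm like 10 mm. When few patients lie above the cut, one comparison group is also very small. Objective 2 asks whether migration matters to the patient, which is part of the rationale for preventing it. If satisfaction declines gradually with displacement, a test that rests on a handful of migrated patients may miss the decline, and the result may be reported as no effect on satisfaction. The readings that could show it will already be in the data set.

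**Working it through.** **The protocol's own figure.** Sample Size gives means of 2.49 and 3.24 mm, variance 1, 80% power and a two-sided 5% level. Then n per group = 2 × (1.960 + 0.842)² × 1 / 0.75² = 27.9, so 28 per group and 56 in total, as stated. With two leads per patient, 56 may mean 56 leads in 28 patients or 56 patients. Both are carried below.

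**Share of patients migrated.** The protocol does not define this, so two readings are used.
- Sample Size says "Lead migration is estimated to occur at a rate of about 13.2"%, without saying per lead or per patient. Taken per patient, it gives 0.132 × 56 = 7.4 or 0.132 × 28 = 3.7 migrated patients. Taken per lead, with independent leads and either lead counting, it gives 1 − 0.868² = 24.7%.
- Assume normal migration with the stated means and SD 1. The chance of exceeding 4 mm is 1 − Φ(0.76) = 22.4% for suture and 1 − Φ(1.51) = 6.6% for Dermabond plus suture. Either lead exceeds 4 mm in 27.4% of patients at between-lead correlation 0, 25% at 0.5 and 23% at 0.8.

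So 13.2% and about 25% are the working values.

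**Information kept under a linear effect.** For a normal exposure cut so that a share p lies above the cut c, the fraction kept is φ(c)² / [p(1 − p)].
- p = 0.132: c = 1.117, φ = 0.2138, so 0.0457 / 0.1146 = 0.40.
- p = 0.247: c = 0.685, φ = 0.3154, so 0.0995 / 0.1858 = 0.54.
- p = 0.275: 0.56.

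These fractions do not depend on the slope.

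**Power.** The correlation r between migration and satisfaction is assumed, because none is stated. Power ≈ Φ(atanh(r)·√(N − 3) − 1.96). For the split, r is multiplied by the square root of the fraction kept: 0.632 at 13.2%, 0.732 at 24.7%. Example with N = 56, r = 0.4 and 13.2% migrated:
- using mm: Φ(0.4236 × 7.280 − 1.96) = Φ(1.12) = 87%
- using the split (r = 0.253): Φ(0.2582 × 7.280 − 1.96) = Φ(−0.08) = 47%

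Loss in percentage points:

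| Patients, share migrated | r = 0.2 | 0.3 | 0.4 | 0.5 |
|---|---|---|---|---|
| 56, 13.2% | 16 | 33 | 40 | 32 |
| 56, 24.7% | 13 | 25 | 28 | 18 |
| 28, 13.2% | 8 | 18 | 31 | 41 |
| 28, 24.7% | 6 | 14 | 24 | 30 |

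Simulation of the t-tests agrees to within about 2 points and puts the largest cell at about 42.

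**One concrete case.** Take the larger of the two leads as the exposure, the stated means and SD, an assumed fall of 0.45 SD in satisfaction per mm, and 56 patients. Simulated power (40,000 runs per setting) at between-lead correlation 0, 0.5 and 0.8 is 78.5, 85.6 and 88.4% using mm, against 53.4, 59.4 and 60.2% using the split. The loss is about 25 to 28 points.

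**The reverse case.** Suppose instead that satisfaction drops by 0.8 to 1.0 SD only beyond 4 mm. With 56 patients and the same exposure, power is 41 to 66% using mm and 68 to 89% using the split, so the split gains about 24 to 29 points. At 13.2% migrated the gain is about 27 to 34 points.

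**The case against.** The strongest objection is that the direction of the gain depends on an unknown shape. A step at 4 mm would reverse it by a similar amount. The Background treats migration as an event that can make the prognostic test fail technically, which is compatible with a threshold. This stands as a limit on the claim. It does not justify 4 mm, for which no section gives a reason, and it does not favour a two-group test as the only stated analysis.

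Second, the Analytical Plan's regression, and its allowance for other analyses, could use millimetres. That also stands: a graded analysis is not excluded. But it is not committed to either, while the objective and the outcome are both worded as two groups. Choosing the form of the exposure after seeing the data would be open to selection.

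Third, this is a secondary outcome with no stated power. That is true, and it limits the weight of the point.

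A reader might infer more than the documents support:
- **That Objective 1 is also planned on a split.** Its wording states none. The outcome (more than 50% relief) is yes/no, but the exposure is left open.
- **That the protocol applies 4 mm to patients.** That sentence concerns the securing methods, and the either-lead rule used above is an assumption of this check.
- **That a fixed number of power points is lost.** No single figure follows from the protocol.

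**Conclusion.** The point holds for Objective 2 and the satisfaction outcome. Their two-group wording discards part of a measurement that is already taken, and patient-level migration is not defined. Under a graded effect the split keeps about 40% to 55% of the information. The power loss is roughly 6 to 42 points across the assumed correlations, the two readings of 56, and 13% to 25% migrated. These figures assume a linear effect and a roughly normal exposure, and they reverse under a pure step at 4 mm. Objective 1 contains no error on this point; its exposure is simply unspecified. The primary comparison of securing methods and its sample size are unaffected. This is an inexpensive improvement to a secondary analysis that should be made.

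**What to change.** In Additional Objectives item 2, the Patient satisfaction outcome and the Analytical Plan:
- Define one patient-level migration measure in millimetres, for example the larger of the patient's two leads.
- Name it as the continuous main predictor of satisfaction in a linear regression, and report the effect per mm with a 95% CI. Name the satisfaction score in the same edit.
- Keep more than 4 mm versus 4 mm or less as a supporting comparison, using the same patient-level measure.

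For consistency, Objective 1 can use the same measure in a logistic regression of the more-than-50%-relief outcome, with that definition unchanged.

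The cost is a wording change; no new patients, images or readings are needed. The downside is lower sensitivity of the main analysis if the effect is a pure step at 4 mm, which is why the supporting comparison is kept.

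### The planned regression and ANOVA take no account of the patient, so a fit with one row per lead would overstate the evidence for patient-level predictors of migration, trial length included

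*Combined protocol and SAP*

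**What the plan says.** Under Interventions and Interactions, each patient has two leads: "1 lead being secured with a suture only while the 2nd lead will be secured after placement with both a suture in addition to Dermabond". The section adds "In this manner, the patient will serve as their own control" and "This is within participant randomization". Migration is measured in millimetres on each lead, and the primary outcome is "Migration rate of trial leads anchored with Dermabond + suture versus suture alone".

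The same section lists the patient data to be collected: "Age, BMI, height, weight, race, ethnicity, history of spine surgery, sex at birth". Each of these is identical for a patient's two leads. Additional Objective 3 asks whether trial lengths of 5, 6, 7 and 8 days differ in migration. If both leads come out together, trial length is also one value per patient. (The description of the matching secondary outcome refers to infection. This point relies on the objective and the outcome's title, which both name migration.)

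For analysis, the Analytical Plan names chi-square tests, t-tests or ANOVA, and then "Regression analysis will be performed to identify independent outcome predictors". It mentions no paired test, patient effect, clustered standard error or per-patient summary. A closing clause allows other inferential methods where suitable, without naming any.

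**The concern.** The design rests on the idea that a patient's two leads share causes of movement. The protocol wants to limit "confounding factors between patients that may predispose them to migration based on body habitus, sheer forces of back musculature" and other physical attributes. That is an argument for a positive correlation between the two leads of a patient, although it is hedged and gives no size.

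With positive correlation, two lead rows carry less information about a patient's BMI, or about the number of trial days, than two independent patients would. An ordinary regression or ANOVA on lead rows ignores this. Its intervals for patient-level factors are too narrow and its p-values too small, so the trial could report an independent predictor of migration, or an effect of trial length, that is not there.

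Making the main comparison paired would not cure this. Patient-level factors cancel out of the within-patient difference, so their effect on migration has to be estimated in a separate model that needs its own treatment of the patient.

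**Working it through.** **How the plan treats leads.** Inputs from Sample Size: means of 2.49 and 3.24 mm (difference 0.75 mm), variance 1, two-sided 5%, power 80%. The independent-groups formula gives n per group = 2 × (1.96 + 0.8416)² × 1 / 0.75² = 27.9, rounded up to 28. The total is 28 + 28 = 56, which is the plan's figure. It therefore assumes no correlation between leads. Whether 56 means leads (28 patients) or patients (112 leads) is unclear, so both are carried below.

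**Size of the error for a patient-level factor.** Let σ² be the residual variance of one lead, r the residual correlation between a patient's two leads, and S the sum of squares of the predictor over patients.

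- An ordinary fit on lead rows reports the slope variance as σ² / (2S).
- The mean of two leads has variance σ²(1 + r)/2, so the true slope variance is σ²(1 + r) / (2S).
- The true standard error is √(1 + r) times the reported one, and the real error rate of a nominal 5% test is 2 × P(Z > 1.96/√(1 + r)).

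The documents give no r, so a range is assumed. The simulations used 20,000 runs per setting: normal data, a securing-method term, one patient-level predictor and no true predictor effect.

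| Assumed r | √(1 + r) | Formula | Simulated, 28 patients | Simulated, 56 patients |
|---|---|---|---|---|
| 0 | 1.00 | 5.0% | 4.9% | 5.1% |
| 0.1 | 1.05 | 6.2% | not run | not run |
| 0.3 | 1.14 | 8.6% | 8.7% | 8.2% |
| 0.5 | 1.22 | 11.0% | 11.1% | 10.9% |
| 0.8 | 1.34 | 14.4% | 14.7% | 14.3% |

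The number of patients hardly matters.

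**One row per patient.** Regressing the mean of the two leads on the predictor gave 4.6% to 5.2% across r from 0 to 0.8 and both sample sizes. A four-group ANOVA on patient means, as would suit trial length, also held about 5%.

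**Securing method.** This factor varies within the patient, so the variance ratio is 1 − r and the error rate is 2 × P(Z > 1.96/√(1 − r)). That is 1.9% at r = 0.3 and 0.6% at r = 0.5, so the test is conservative.

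**Events for migration above 4 mm.** At the plan's 13.2%, 56 leads give 56 × 0.132 = 7.4 events and 112 leads give 112 × 0.132 = 14.8.

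**The case against.** The strongest reply is that the Analytical Plan never says the regression is on leads. Its outcome could be response or satisfaction, each recorded once per patient, and then nothing is counted twice. That is correct. A reader might infer that the plan specifies a wrong model, but the text supports only that the model is unspecified. The risk is still real: the primary outcome exists only per lead, Objective 3 sets a patient-level factor against it, the sample size treats leads as independent, and no method that recognises the patient is named.

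A second reply concerns size. A reader might take an inflation to 8% to 14% as a property of this trial. It is not, because it rests on an assumed r. The protocol's remark that patient attributes may "predispose them to migration based on body habitus, sheer forces of back musculature, and other physical attributes that could augment lead migration" supports the sign of r, not its value. What counts is the correlation left after covariates, and BMI, height and weight may absorb part of it. If covariates explained half the shared variance, r = 0.5 would become 0.25/0.75 = 0.33 (about 9.0%) and r = 0.3 would become 0.15/0.85 = 0.18 (about 7.1%). This objection stands, and it is why the range starts at 0.1.

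A reader might also multiply the error over all eight listed variables. With eight unrelated predictors, simulation gives a 49% to 72% chance of at least one false finding for r from 0.3 to 0.8, against 28% to 32% with the patient as the unit. That overstates the present point. About 30 percentage points are ordinary multiplicity, which accounting for the patient does not remove, and the eight are not unrelated, since BMI is computed from height and weight.

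Finally, no stated objective asks for demographic predictors of migration, so that part is exploratory. This is fair, but trial length is tied to a stated objective.

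**Conclusion.** The point holds conditionally. If migration is analysed with one row per lead and no allowance for the patient, tests of patient-level factors have a false-positive rate of about 6%, 9%, 11% and 14% at an assumed residual correlation of 0.1, 0.3, 0.5 and 0.8. This applies to each single-coefficient test of a patient-level factor. The four-group comparison of trial lengths on lead rows has the same fault. It does not apply to outcomes measured once per patient, and it does not mean that the securing-method comparison is prone to false positives, since there the error runs the other way.

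Severity is minor to moderate: the primary comparison is untouched, but a secondary objective and any reported predictors are exposed.

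**What to change.** Replace the regression sentence in the Analytical Plan with text such as:

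> Predictors of lead migration in mm, including trial length, will be analysed in a linear mixed model with a random intercept for patient, fixed effects for securing method, side and the prespecified predictors, and degrees of freedom based on the number of patients. For patient-level factors alone, the mean of the patient's two leads may instead be regressed on the predictors, one row per patient. Response and satisfaction will be analysed with one row per patient.

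For migration above 4 mm, use a patient-clustered model (for example GEE logistic) with a small-sample correction, limited to securing method and at most one or two prespecified predictors. Otherwise report it descriptively, because 7 to 15 expected events cannot support all the listed covariates.

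The cost is a few sentences and standard software, with no new data or patients. The downside is wider, but correct, intervals for patient-level factors, and fewer predictors in the binary model.
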